7.1. RAPTOR f feasibility design

This is a multi-centre, open-label, randomised two-arm parallel feasibility study. Aiming to assess the feasibility of a full-scale randomised study of RAPID driven treatment of pleural infection versus standard care.

Once participants are diagnosed with pleural infection, based on well-recognised diagnostic criteria in accordance with the evidence-based recent national British Thoracic Society guidelines(BTS 2023)(1), they are allocated to either the standard care group, who receive pleural infection management as per BTS guideline 2023) (1), or the intervention group, who receive treatment which is driven according to the baseline calculated RAPID score (see below).

Participants with suspected pleural infection will be approached initially by the clinical team as inpatients. Enrolment will occur within 24 hours of confirmation of the diagnosis of pleural infection and / or chest drain insertion using standard criteria for the diagnosis of pleural infection as per BTS guidelines (1).

The RAPID score

For participants allocated to the RAPID driven treatment arm only, the risk stratification "RAPID score" will be calculated at the time of presentation according to the parameters in Table 1. According to the calculated RAPID score, subsequent treatment will proceed (see below).

Parameter	Me	asure	Score
R enal	Serum Urea Level	< 5 mmol/L	0
		5 – 8 mmol/L	1
		>8 mmol/L	2
A ge	Age	< 50 years	0
		50 – 70 years	1
		> 70 years	2
P urulence of fluid	Purule	ent fluid	0
	Non-pur	1	
Infection source	Communi	ty-acquired	0
	Hospital	-acquired	1
D ietary factors	Serum albumin level	>27mmol/L	0
		<27mmol/L	1
Risk categories	Low risk	Moderate risk	High risk
	0-2	3-4	5-7

Table 1:The RAPID risk–prediction score (7,12)

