9. PROTOCOL PROCEDURES

The following table illustrates scheduled study related procedures and data collection

Procedure		Consent	Innetions	Follo	ow up visits		
	Screening	Baseline/ Randomisation	Inpatient Assessme	3 days¹	14 days	28 days	90 days
			nt(s)	+/- 2 days	+/- 3 days	+/- 3 days	+/- 3 days
Eligibility assessment	X	Х					
Informed consent	X ²	X ²					

Demographics R	х	Х					
Medical history ^R	Х	Х					
Clinical assessment R	Х	X	Х	X	Х	Х	Х
Concomitant medication ^R	X3	X ³					
Imaging routine – chest x ray R		Х			Х	Х	Х
Imaging routine – Thoracic Ultrasound ^R		Х	X (on days 3±1 and 5±1 post randomisatio n)	X	X	X	
Imaging routine – CT chest ^R	X ⁴	X ⁴	X ⁴				
Chest drain insertion or therapeutic aspiration in situ or planned	х	X					
Intrapleural enzyme therapy ^R			х				
Surgery ^R			Х				
Routine clinical bloods	Х	Х	х	Х	х	Х	
Routine pleural fluid ^R	Х						
Randomisation		X					
RAPID score		X ⁵					
Research pleural fluid collection and storage		Xe	X ₆				
Research blood collection and storage		X ⁶	X _e				
Breathlessness and/or pain (VAS) score		X ⁷			X ⁷	X ⁷	X ⁷

QOL: EQ-5D-5L	X ₈			X8	X8	X8
---------------	----------------	--	--	----	----	----

Assessment of functional ability (SF36)			X 9	X 9	X ⁹
Health utilization		Х			
Semi- structured interviews				X ¹⁰	

^R Indicates procedures or data collection that is part of routine care for all patients. The results of these are required to be collected and documented as part of the RAPTOR - f study, hence are included in this table.

¹ This will be applied to the low RAPID score group, please see the protocol for the details

² Informed consent will be taken within the first 24 hours after discussing the study and offering the participant information sheet.

³ If the participant had any antibiotics prior to admission to the hospital or if they are on anticoagulation or antiplatelet.

⁴ CT scan will be conducted as part of the usual care for all participants with pleural infection during the inpatient stay

⁵ The RAPID score will be calculated for the intervention group ONLY following randomisation.

⁶ The research samples (paired pleural fluid and blood) will be collected on day 1 (randomisation day) 0,3 and 5 post- randomisation (with the first week). This is optional, please see the protocol for the details of the process.

⁷ These assessments will take place in person at baseline, 14 days +/- 3, 28 days +/-3 days and remotely in 90 days +/- 3 days, please see protocol.

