9.4. Baseline assessment

Patients who are willing to participate in the study will have a baseline assessment performed by a member of the research team and documented into relevant CRF. The baseline data will be collected while the participant is in hospital and completed before the patient is discharged. This will include a collection of the following data onto an electronic CRF (REDCap) as follows:

[figure not shown]
- 1. Confirmation of the inclusion and exclusion criteria
- 2. Participant demographics
- 3. Relevant medical history:
 - Co-morbidities (at enrolment) including the presence of chronic renal failure or bleeding disorder
 - Details of the symptoms the participant has had for the current pleural infection (at enrolment) including length of symptoms and nature of the infection (community or hospital acquire infection)
 - Uses of antibiotics before admission to hospital e.g. types and duration
 - Details of the treatment that the participant has had for the current pleural infection (at enrolment i.e. antibiotics, chest drain insertion or therapeutic aspiration)
 - Current medications including antiplatelets and anticoagulants
 - Recent blood test results as part of usual clinical care where available (within 1 week prior to randomization)
- 4. Details of recent radiology results including CXR, and first TUS to be uploaded (videos and images where available) (within 1 week prior to randomization)

5. CT chest will be transferred in a secured USB, Compact Disk or other appropriate password-protected device to Oxford Centre to assess for a radiological pattern of pleural infection e.g., consolidation (within 1 week prior to randomisation)

6. EQ-5D quality of life questionnaire, VAS for chest pain and shortness of breath

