9.5. Randomisation

Following consent and baseline assessment, randomisation will occur via a secure web-based system Sealed Envelope by a member of the RAPTOR f research team at the site. Randomisation will occur once the pleural infection has been confirmed by the documented inclusion criteria. This may occur after the therapeutic pleural aspiration or once a chest drain has been inserted or with a high suspicion of pleural infection. Participants will be randomly allocated to one of two arms of the study in a 1:1 ratio to either standard care or RAPID-driven treatment, see study flow diagram (Chart 1). Randomisation will be randomly generated by the Sealed Envelope software to reduce selection bias.

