9.6. Blinding and code-breaking

There is no blinding in this study, hence no un-blinding procedures or code-breaking are required.

9.7. Description of study intervention(s), comparators and study procedures (post-randomisation and inpatient period)

Intervention arm

In the intervention arm, treatment will be determined according to the calculated baseline RAPID score.

Patients with a higher RAPID score (and thus higher predicted mortality and morbidity (7,12)) will be triaged to more aggressive treatment early in the disease, and those with lower predicted mortality and morbidity will be treated less aggressively.

A. Low risk (RAPID score 0 to 2):

Patients will be treated as follows:

- 1. Pleural drainage: therapeutic pleural aspiration (drain to dryness) using a Rocket kit will be suggested as the initial treatment. If the patient has already had a chest tube inserted prior to randomisation (as randomisation can occur for 24 hours after drain insertion), then patients will be admitted for drainage for a proposed maximum of 24 to 48 hours, with the removal of the drain as soon as possible, provided there is no residual collection of pleural fluid on the chest-xray (CXR) or thoracic ultrasound or CT scan before drain removal. No specific size of drain is specified, and local practice should be followed.
- 2. **Broad spectrum antibiotics**: see below for the expected standard of care in both intervention groups concerning antibiotics, which are as per NHS standard care for pleural infection. Use of early oral antibiotics to promote discharge is recommended in this group.
- 3. **Review at 3 days +_ 2 days post-discharge** with bloods including full blood count, CRP (Creactive protein), liver and renal profile, ultrasound scan and chest x ray.
- 4. **Patient contact:** All patients will receive a 24-hour contact number (to the study fellow) who can be contacted should there be any concern or deterioration when at home which will prompt urgent review by the pleural service locally.

If at any point a patient is considered to have *failed treatment* on the basis of predefined criteria (see below), they will then be treated as per the intermediate/high-risk group below and will be admitted to hospital.

B. Intermediate + high-risk (RAPID score 3 to 7)

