The intermediate and high-risk groups have been combined for the treatment algorithm; there are similar numbers of patients in the combined intermediate and high risk group and the low-risk group (7). Patients in this category will be treated as follows:

- 1. **Pleural drainage:** all patients will be admitted to hospital for chest drain insertion and remain in hospital for as long as is clinically required while the tube is in situ. No specific size of drain is specified, and local practice should be followed.
- 2. Broad spectrum antibiotics: see below; IV antibiotics can be given while the patient is admitted.
- 3. Adjunctive therapy:
 - a. Intrapleural enzyme therapy (tPA / DNase) should be started as soon as possible after drain insertion and randomisation, assuming there are no contraindications. if there is no risk of bleeding.

b. In parallel, referral to local thoracic surgical services made at the time of randomisation, and the need for surgery clinically revisited at 48 hours post-randomisation.

c. In patients where there are contraindications to intrapleural enzyme therapy, immediate surgical intervention in suitable patients should be considered.

Standard care arm:

In the standard care group, the RAPID score *will not be routinely calculated*, and all patients will undergo treatment as per current national guidelines (BTS 2023) (1). This is summarized as follows:

- 1. **Pleural drainage:** all patients will be admitted to the hospital for chest drain insertion and subsequent drainage
- 2. Broad spectrum antibiotics: see below
- 3. **Clinical review** of progression will occur 48 to 72 hours after randomisation and initial above treatment. If there is evidence of poor clinical response (on the objective criteria listed below), the patient will be escalated to either intrapleural therapy or surgical intervention according to patient suitability and clinician choice / usual practice.

Treatment applicable to both arms

A number of treatments should be considered best practice and routine management in patients with pleural infection and will be applied to both groups (intervention and standard care). These treatments follow the NHS standard of care for pleural infection and are as follows:

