13.1. Description of the Statistical Methods

13.1.1. Analysis of the RAPTOR f feasibility study:

Feasibility parameters will be measured and reported, and include:

- Recruitment proportion (number of randomised patients divided by number of eligible patients)
- Randomisation acceptance rate (proportion of patients who are willing to be randomised over those eligible)
- Retention (number of participants who complete intended treatment, number of participants who complete intended follow up)

These will be reported and used to assess whether or not a definitive trial is feasible. Descriptive statistics will be used to describe the demographic characteristics between the two groups. For categorical variables, numbers (and proportions) will be reported for each treatment group and overall. For continuous variables, means and standard deviations (or medians in the interquartile range) will be reported for each treatment group and overall. As this feasibility study is not powered to draw definitive conclusions, comparisons between the two arms for clinical outcomes will be reported using descriptive statistics only. No statistical tests will be carried out. These will be based on multivariable linear (for continuous outcomes) or logistic (for binary outcomes) regression with adjustment for stratification factors and important prognostic factors and will be reported as adjusted differences in means (for continuous outcomes) or proportions (for binary outcomes). Treatment comparisons will be reported for the intention-to-treat population (all randomised participants will be analysed according to their allocated treatment group irrespective of which treatment they actually receive) as treatment effects together with 95% confidence intervals for the two main comparisons: (1) Standard care vs overall RAPID driven treatment (2) Low RAPID driven treatment arm vs moderate to high RAPID driven treatment arm. Compliance to the interventions will be reported.

To establish the feasibility of collecting accurate long-term outcomes in randomised participants, we will present the completeness of the outcomes across the duration of the trial. The outcome measures collected in this study will be used to inform the sample size for the future definitive large-scale phase III RCT if it is feasible to be undertaken.

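### Low versus moderate-to-high RAPID within one arm is planned as a treatment effect although it is not randomised, and the randomised within-risk comparisons are not planned

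*Protocol*

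**What the plan says.** Section 13.1.1 (Protocol) says that comparisons for the intention-to-treat population will be reported "as treatment effects together with 95% confidence intervals for the two main comparisons". The first is standard care versus RAPID-driven treatment overall. The second is "Low RAPID driven treatment arm vs moderate to high RAPID driven treatment arm". The synopsis also lists a comparison between groups within the RAPID arm as a comparator. Section 13 opens by saying that no separate SAP will be used, so this is the operative analysis text.

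Section 9.5 allocates participants "in a 1:1 ratio to either standard care or RAPID-driven treatment"; nobody is allocated to a risk group. Section 9.7 explains how risk group sets care: "Patients with a higher RAPID score (and thus higher predicted mortality and morbidity (7,12)) will be triaged to more aggressive treatment". Low risk is a score of 0 to 2, and intermediate plus high risk is 3 to 7.

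Three places confine the score to one arm. Section 7.1 introduces it with "For participants allocated to the RAPID driven treatment arm only, the risk stratification". Footnote 5 to the schedule in section 9 says: "The RAPID score will be calculated for the intervention group ONLY following randomisation". Section 9.7 says that under standard care the score "will not be routinely calculated".

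Section 9.4 collects, for all participants, demographics, the setting of the infection and "Recent blood test results as part of usual clinical care where available (within 1 week prior to randomization". Albumin, one of the five RAPID components, is not named there.

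**The concern.** A reader of the trial report will take a main comparison labelled a treatment effect to estimate what treatment did. Comparison (2) does not. Its two groups differ by design in predicted mortality and morbidity, and they also receive different care, so the difference between them reflects both.

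The clinically useful questions are whether low-risk patients do better on the low-risk pathway than comparable patients under standard care, and likewise for moderate-to-high risk. Randomisation supports both, but neither is planned, and both require RAPID to be known for controls.

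This bears on the next trial. Section 13.1.1 says that outcomes collected here will inform its sample size, and section 13.2 builds that size on an 8-day reduction in low-risk patients. That reduction is a low-risk, between-arm quantity. The plan never estimates it, and comparison (2) could be mistaken for it.

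**Working it through.** **1. The plan's own figure.** Inputs from section 13.2: difference 4 days, SD 10, 5% significance (two-sided assumed; sidedness is not stated), 90% power.

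n per arm = 2 × (1.96 + 1.2816)² × 10² / 4² = 131.3, rounded up to 132, so 264 in total. The stated figure reproduces. The 4 days is 50% low-risk × 8 days, which implies no effect on stay in the other half.

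**2. What each contrast estimates.** Let the mean stay under standard care be L for low risk and L + d for moderate-to-high risk. Let the pathway effects be e_L and e_H.

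- Low versus low, between arms: e_L
- Moderate-to-high versus moderate-to-high, between arms: e_H
- Comparison (1), at 50% low-risk: (e_L + e_H) / 2
- Comparison (2): (L + e_L) − (L + d + e_H) = e_L − e_H − d

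Comparison (2) equals the low-risk treatment effect only if d = 0 and e_H = 0. The documents do not give d, so the values below are assumptions. The last column uses section 13.2's implied effects, e_L = −8 and e_H = 0.

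| d (days, assumed) | Comparison (2) if the pathways do nothing | Comparison (2) if e_L = −8, e_H = 0 |
|---|---|---|
| −4 | +4 | −4 |
| 0 | 0 | −8 |
| 4 | −4 | −12 |
| 8 | −8 | −16 |

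In the last column the randomised contrasts stay at −8 (low), 0 (moderate-to-high) and −4 (overall), whatever d is.

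**3. Whether adjustment helps.** Section 13.1.1 adjusts for important prognostic factors. The score defines the groups, so no score value occurs in both. Separating risk from treatment would rest entirely on a model extrapolating across the cut-off between 2 and 3.

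**4. Precision.** Half-width = t × SD × √(1/n₁ + 1/n₂), with SD 10 and 15 per arm split about evenly by risk.

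- Comparison (1), 15 versus 15: 2.048 × 10 × √(2/15) = ±7.5 days
- Comparison (2), 7 versus 8: 2.160 × 10 × √(1/7 + 1/8) = ±11.2 days
- Within-risk contrasts: ±11.6 days for 7 versus 7, ±10.7 days for 8 versus 8

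**5. Chance imbalance on RAPID in comparison (1).** The score is calculated after randomisation, so allocation cannot be stratified on it. With two independent Binomial(15, 0.5) counts, the arms differ by at least 3 low-risk patients with probability 0.36, and by at least 4 with probability 0.20.

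**6. The definitive trial.** Detecting 8 days within the low-risk group at 90% power needs 2 × (1.96 + 1.2816)² × 100 / 64 = 32.8, so 33 low-risk patients per arm. At 132 per arm and 50% low-risk there would be 66.

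**The case against.** The strongest reply is that this is a 30-patient feasibility study. Its primary outcome is willingness to be randomised and interviewed, and none of the eight progression criteria in section 13.1.2 uses a clinical comparison. Section 13.1.1 says that the study is not powered for definitive conclusions and that no tests will be done. All of that stands, and it limits the severity.

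Several stronger readings are tempting, but the documents do not support them.

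- *The within-risk contrasts are lost, or balance on risk cannot be checked.* Age, infection source and usual-care bloods are collected in both arms, and purulence is one of the alternative eligibility features. Restricting calculation of the score during care does not bar deriving it later, and the planned adjustment does not exclude its components. What is missing is a plan to derive it, and assurance that urea and albumin will be available.
- *RAPID is known to predict length of stay.* Section 5 supports prediction of 3-month mortality, and section 9.7 adds morbidity. No stay by risk group is given, so d is an assumption and could be zero.
- *The ±11 days counts against comparison (2) in particular.* It is sampling error, separate from the bias, and it applies equally to the contrasts proposed here.
- *Scoring controls would secure the definitive sample size.* The total does depend on the low-risk share (412 at 40%, 730 at 30%, if the 8 days holds). But the intervention arm already estimates that share. Scoring all 30 narrows the half-width only from 25 to 18 points; 32% to 68% does not separate 264 from 412.

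**Conclusion.** The point holds. Comparison (2) is not randomised, cannot be repaired by covariate adjustment, and should not be called a treatment effect. The distortion in expected stay is −d − e_H days relative to the low-risk effect, which is 0 to −8 days over the assumed range d = 0 to 8 with e_H = 0. Its true size cannot be taken from the documents. For mortality, the protocol's own premise that the score predicts death means that a gap should appear even if the pathways change nothing.

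The valid within-risk contrasts are not planned, and they are possible only if RAPID is derived for controls. This should be fixed, but it does not threaten the feasibility conclusions. With 7 to 8 patients per cell, the benefit is a correctly defined estimand and a template for the definitive trial, not an answer from these 30 patients.

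**What to change.** In section 9.4 and the eCRF, list urea, albumin, age, purulence and infection source as required baseline fields in both arms. Take the values from usual care, and record a reason where one was not measured.

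In sections 7.1, 9 (footnote 5) and 9.7, state that RAPID will also be derived centrally for standard-care participants, for analysis only and not shown to treating clinicians.

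In section 13.1.1:

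- replace comparison (2) with standard care versus RAPID-driven treatment within low risk and within moderate-to-high risk, each with a 95% confidence interval and described as exploratory;
- name RAPID category as a prognostic adjustment factor in comparison (1);
- present low versus moderate-to-high within the RAPID-driven arm as descriptive summaries only, and align the comparator entry in the synopsis.

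The cost is a few more required control-arm fields, one derived variable and some rewording. Care in either arm is unchanged. It is best done while recruitment is open, because a baseline blood result that was not recorded may not be recoverable later.

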2. LAY SUMMARY

2.1. Background

Pleural infection is a common and serious complication of infection in the lung (pneumonia), which results in a collection of fluid between the chest wall and the lung. It affects more than 65,000 patients each year in the United States (US) and the United Kingdom (UK), and in the UK there are 40 new cases per day. The disease is fatal in 20% of people, and patients stay in hospital for an average of 13 days for treatment. The cost of treatment in the NHS is approximately £4000 per patient, equating to £58 million per year.

Standard treatment for pleural infection includes antibiotics and drainage of the fluid through a tube inserted between the ribs (chest drain). When patients do not respond to initial treatment, surgery is sometimes required. Alternatively, medications can be given through the chest drain which clears out the infected material (called Intrapleural Enzyme Therapy or IET). This treatment has been shown to reduce hospital stays and the need for surgery. Surgery is an effective treatment, but it has several side effects and is not an option for very unwell patients and the elderly, where the death rate is 40%.

Being able to predict which patients are most vulnerable to a bad outcome from a pleural infection (i.e. need surgery or die) at the start of treatment would be very valuable. This would help us to identify the sickest patients and offer the best treatment option as early as possible. Our group has developed a simple score (called RAPID) which uses information routinely collected in clinical care. We have proven that RAPID is reliable in identifying those at the highest risk of death and bad outcomes. What we do not know is whether we can use the RAPID score to inform treatment decisions and therefore benefit patients. To prove this, we need to conduct a large study. Before doing this, it is essential that we conduct a smaller pilot study to know such a large study would be possible, and that selecting the best treatment option according to RAPID score is acceptable to patients and doctors.

2.2. Study design and methods:

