This pilot study will recruit 30 patients who are in hospital with a confirmed pleural infection from 4 UK centres over an 8 to 10 month period. The patients will be randomised (assigned by computer) to the standard treatment pathway or treatment driven by the RAPID risk stratification score. We will follow patients for up to 3 months. We will measure whether this approach to treatment decisions is acceptable to patients and doctors and whether the study answers the key questions. This will help us know if a larger, definitive study is possible.

We will also interview around 12 patients who are willing to be part of the study, and some who decide not to participate to understand what is important to them when treating this disease and their reasons for taking part or not. Additionally, we will interview 6 clinicians to assess their views and the acceptability of the study and to explore any barriers to participation. This will help us understand what should be measured in a larger study to best improve patient care.

We will collect pairs of pleural fluid and blood from all RAPTOR-f participants to measure the biomarkers and assess for microbiology alongside the septations score on the ultrasound scan to evaluate whether rising levels of these biomarkers will predict treatment failure for patients with pleural infection.

The biomarkers include suPAR (Soluble Urokinase Plasminogen Activator Receptor), PAI-1 (Plasminogen-Activator Inhibitor-1), NE (Neutrophil Elastase) and cytokines interleukins (IL) 1 and 2 on both blood and the pleural fluid.

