Adverse events and serious adverse events will be reported by each arm in the intervention group on the safety population only (all patients who received the allocated treatment).

It is anticipated that STATA (StataCorp LP) or other appropriate validated statistical software will be used for analysis.

13.1.2. Analysis of the embedded qualitative:

Interviews will be digitally audio-recorded, transcribed verbatim, and de-identified before being uploaded to data management software. The interview data will be analysed using Thematic Analysis. Audio-recordings will be listened to, and transcripts read and re-read for familiarisation, then opencoded to develop an initial code list. Codes will then be grouped into categories, and data explored to identify connections and to develop a descriptive account of the dataset as a whole. The analysis will

focus on the acceptability of study processes to patients, individual and group equipoise, and the patient experience of pleural infection and treatment.

For the RAPTOR-f study and embedded qualitative interviews, we will use robust progression criteria (see Table 1) to assess the feasibility of progression to a definitive phase III trial; green indicates all criteria are met, and if met, a larger study will be declared feasible. If one or more criteria are amber, this will result in mitigations including:

- o Review of qualitative data to identify barriers and potential mitigations
- o Discussion of recruitment to date and barriers with the study management group
- o Consideration of widening the recruited population and increasing centres

Table 1: Illustrate stop and go criteria for study progression, this will be applied for all centres, if any criteria are red, this will prompt major changes to the study or qualitative study design.

Criteria	Green	Amber	Red
Recruitment proportion (number eligible versus number randomised)	>50%	30% - 50%	< 30
Average monthly recruitment* (pts/centre/month)	≥1.0	0.5 – 0.9	< 0.5
Adherence to the allocated intervention group	≥90%	75% - 90%	< 75%
The proportion of key date completion (e.g Visual Analogue Score)	≥98%	75% - 97%	< 75%
Proportion completing study protocol (accounting for 10% expected attrition)	≥90%	75% - 90%	< 75%
Individual site recruitment (at 10 months)	≥10	5 – 9	< 5
Proportion completing clinicians' interview	>50 %	30% - 50%	< 30%
Proportion completing patients' interview	>50%	30% - 50%	< 30%

^{*} Once all centres have been greenlighted

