13.2. Sample Size Determination

As a feasibility study, 30 patients are considered sufficient to demonstrate the feasibility of recruitment to a larger study. In addition, a potential sample size calculation for a definitive phase 3 trial is presented below to ensure the correct feasibility parameters of the recruitment rate are robustly addressed in the feasibility study.

The average hospital stay for pleural infection is 14 days (SD 10). Assuming RAPID driven treatment overall reduces hospital stay by 4 days (as 50% of the RAPID arm will be in the low-risk group and reducing the length of stay by 8 days is reasonable as such patients will be sent home within 24 to 48 hours of treatment), and assuming a clinically meaningful difference in hospital stay of more than 4 days

(SD 10 from previous studies), with 5% significance and 90% power, this would require 264 patients in total (132 randomised 1:1). In a definitive study of this design recruiting in 15 centres in the UK over 18 months recruitment, a rate of 1 patient/centre/month would provide sufficient patients.

For the feasibility RAPTOR study, a target of 30 patients in total (3-4 centres recruitment over 10 months at 1 patient/centre/month) is therefore reasonable.

This number should be sufficient to conduct meaningful qualitative interviews with patients/carers (in discussion with our qualitative co-applicant) and is also sufficient to show a definitive study is possible, with careful measurement of the number eligible / number consented / number randomised / number completing protocol.

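### The green threshold of at least 10 patients per site cannot be met by four centres in a 30-patient study, and three centres can meet it at 30 only with an exact 10/10/10 split

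*Protocol*

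**What the plan says.** Section 13.1.2 sets out a green, amber and red table for progression to a definitive trial. On the decision rule it says: "green indicates all criteria are met, and if met, a larger study will be declared feasible". One or more amber rows lead to listed mitigations, and any red row prompts major changes. The criteria are applied to all centres.

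The rows that matter here are:

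- "Individual site recruitment (at 10 months"): green at 10 or more, amber 5 to 9, red below 5.
- Average monthly recruitment per centre: green at 1.0 or more, amber 0.5 to 0.9, red below 0.5. A footnote starts the count once all centres are open.
- "The proportion of key date completion (e.g Visual Analogue Score"): green at 98% or more, amber 75% to 97%.
- "Proportion completing study protocol (accounting for 10% expected attrition"): green at 90% or more, amber 75% to 90%. Adherence to allocation uses the same bands.

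On size, the lay summary (Section 2.2) plans to "recruit 30 patients who are in hospital with a confirmed pleural infection from 4 UK centres over an 8 to 10 month period". Section 13.2 gives "a target of 30 patients in total (3-4 centres recruitment over 10 months at 1 patient/centre/month"). The synopsis and Section 9.1 also say 3 to 4 centres, and Section 9.1 names four. Section 13 states that there will be no separate SAP.

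**The concern.** The table decides whether a definitive trial is declared feasible, and it is the only place where that rule is defined. Its thresholds should therefore be reachable by a study that recruits to its own plan. The per-site count appears to have been set for three centres, while the lay summary and the list of sites describe four. If so, a four-centre study that reaches its target of 30 would still miss green on a row that its sample size rules out. The investigators would then have to run mitigations that the data do not call for, or reinterpret the threshold after seeing the results.

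**Working it through.** **Inputs.** Total 30 (synopsis, Sections 8.1 and 13.2). Centres: 4 (Section 2.2; four named in 9.1) or 3 to 4 (synopsis, 9.1, 13.2). Recruitment 8 to 10 months (2.2, 9.1). Thresholds from the Section 13.1.2 table. Definitive trial: 264 patients, 15 centres, 18 months (13.2).

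**The plan's own figures.** Target = centres x months x rate.

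- Three centres: 3 x 10 x 1 = 30, which reproduces the target.
- Four centres: 4 x 10 x 1 = 40, which does not.

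The definitive-trial figure (difference 4 days, SD 10, two-sided 5% assumed, 90% power) reproduces at 132 per arm, 264 in total. Neither 30 nor 264 is miscalculated; 30 simply belongs to three centres.

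**Site row.** Minimum total for green = 10 x number of centres.

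- Four centres: 10 x 4 = 40 > 30. At most three of the four can reach 10, and the mean is 30/4 = 7.5, which is amber.
- Three centres: 10 x 3 = 30, so at exactly 30 patients only a 10/10/10 split passes. If each patient is equally likely to come from any site, the probability is 30!/(10!³ x 3³⁰) = 0.027.

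**Rate row.** Patients per centre-month, all centres open throughout:

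| Centres | 8 months | 10 months | Time to 30 at 1.0 |
|---|---|---|---|
| 3 | 30/24 = 1.25 | 30/30 = 1.0 | 10 months |
| 4 | 30/32 = 0.94 | 30/40 = 0.75 | 7.5 months |

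Four centres reach green only by finishing in 7.5 months, before the planned window opens.

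**Bands.** In the adherence and protocol-completion rows, 90% is both green and amber. This is not a remote case: 10% attrition from 30 leaves 27/30 = 90% exactly. There are gaps between 0.9 and 1.0 in the rate row and between 97% and 98% in the key-data row.

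**Key-data denominator.** Suppose all 30 randomised participants count and 3 (10%) are lost. Sections 9, 9.9 and 9.10 differ on the VAS time points, so both three and four are shown.

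- Final visit alone: 27/30 = 90%.
- Pooled over three time points: (90 - 3)/90 = 96.7% if only the last is missed; (90 - 6)/90 = 93.3% if all post-baseline ones are missed.
- Pooled over four: (120 - 3)/120 = 97.5% and (120 - 9)/120 = 92.5%.

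All are below 98%. If only assessments due from participants still in follow-up count, 27/27 = 100% is possible. The same data can therefore be green, amber or, at 97.5%, between bands.

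**The case against.** The strongest reply is that three centres are expressly allowed. With three, 3 x 10 = 30 and 30/(3 x 10) = 1.0, so both recruitment rows can be green. This stands. A reader might infer that green is out of reach altogether, and the documents do not support that. The 2.7% also assumes equal site rates and a stop at exactly 30, whereas Section 13.2 calls 30 a target and no per-site cap is stated. Even so, 30 is the stated sample size, and nothing provides for the 40 that four centres would need.

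The rate footnote also has force. If centres open at different times, the count starts only when the last one opens, and four centres might then reach 1.0. The table does not say which patients and months enter, so 0.94 to 0.75 holds only for centres open throughout. A true rate of 0.75 would also be a fair warning, because the definitive plan needs nearly 1.

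On key data, it is tempting to say that 98% contradicts the planned 10% attrition. It does so only if all randomised participants form the denominator. Completing due assessments and completing the protocol are different quantities, so the defect is an unstated denominator.

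A reader might also combine "The disease is fatal in 20% of people" with the 90% completion row and conclude that green is unlikely: P(at most 3 deaths in 30 at 20%) = 12%. That assumes that a disease-level figure applies to this selected population and that deaths count as non-completion. The protocol says neither.

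Finally, some gaps may be rounding: 0.94 printed to one decimal is 0.9, amber. No rounding rule is given, and rounding does not explain the overlap at 90%.

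**Conclusion.** The site threshold is wrong as written for the four-centre design. It needs 40 patients against 30, so at the target size that row cannot be green however well sites recruit. For three centres it is attainable but has no slack. The rate row is in tension with the four-centre calendar (0.94 to 0.75 against 1.0), provided that all centres are open throughout. The overlaps, gaps and missing denominator are smaller defects in the same table, and no separate SAP is planned to settle them.

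The consequence should not be overstated. Under four centres the rule forces at least amber, and amber brings mitigations. It does not stop the study. Nor does it alter the separate primary success definition (at least 50% of eligible patients willing to be randomised and at least 50% agreeing to interviews). A reader might infer that the study can no longer answer its feasibility question, but that does not follow.

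**What to change.** Amend the Section 13.1.2 table and align Sections 2.2, 9.1 and 13.2 with it.

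- **Centres, per-site count and total.** State the number of centres on which 30 rests. Either drop the absolute per-site count or scale it to 30 divided by the number of open centres (7.5 for four, 10 for three) with some slack below that mean, and reset the amber and red bands to match.
- **Rate.** Define it as patients randomised per open centre-month up to the 30th randomisation. Keep the cut at 1.0, because the definitive plan needs 264/(15 x 18) = 0.98. Four centres over 8 to 10 months would still be amber on this row, but that would be a real signal about recruitment.
- **Bands.** Make them contiguous and non-overlapping, for example 1.0 or more, 0.5 to below 1.0, below 0.5; and 90% or more, 75% to below 90%, below 75%. Treat the key-data row in the same way.
- **Key data.** State that completion is computed over assessments due from participants alive and not withdrawn.

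Lowering the 98% cut, or counting death as protocol completed, would be a matter of preference and is not required. The cost is a protocol amendment and a less demanding per-site target. No new patients or data are needed, and the change should be made before results are seen.
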